15. PHARMACOVIGILANCE

15.1 DEFINITIONS

Adverse Event (AE): any untoward medical occurrence in a patient or clinical trial subject administered a medicinal product and which does not necessarily have a causal relationship with this treatment. *An AE can therefore be any unfavourable and unintended sign (including an abnormal laboratory finding), symptom, or disease temporally associated with the use of an investigational medicinal product (IMP), whether or not considered related to the IMP.*

Adverse Reaction (AR): all untoward and unintended responses to an IMP related to any dose administered. *All AEs judged by either the reporting investigator or the sponsor as having reasonable causal relationship to a medicinal product qualify as adverse reactions. The expression reasonable causal relationship means to convey in general that there is evidence or argument to suggest a causal relationship.*

Unexpected Adverse Reaction: an AR, the nature or severity of which is not consistent with the applicable product information (eg investigator's brochure for an unapproved investigational product or summary of product characteristics (SmPC) for an authorised product). *When the outcome of the adverse reaction is not consistent with the applicable product information this adverse reaction should be considered as unexpected. Side effects documented in the SmPC which occur in a more severe form than anticipated are also considered to be unexpected.*

Serious Adverse Event (SAE) or Serious Adverse Reaction: any untoward medical occurrence or effect that at any dose

Results in death

Is life-threatening – refers to an event in which the subject was at risk of death at the time of the event; it does not refer to an event which hypothetically might have caused death if it were more severe

Requires hospitalisation, or prolongation of existing inpatients' hospitalisation

Results in persistent or significant disability or incapacity

Is a congenital anomaly or birth defect

Medical judgement should be exercised in deciding whether an AE/AR is serious in other situations. Important AE/ARs that are not immediately life-threatening or do not result in death or hospitalisation but may jeopardise the subject or may require intervention to prevent one of the other outcomes listed in the definition above, should also be considered serious.

Suspected Unexpected Serious Adverse Reaction (SUSAR): any suspected adverse reaction related to an IMP that is both unexpected and serious.

15.2 CAUSALITY

Most adverse events and adverse drug reactions that occur in this study, whether they are serious or not, will be expected treatment-related toxicities due to the drugs used in this study. The assignment of the causality should be made by the investigator responsible for the care of the participant using the definitions in the table below.

If any doubt about the causality exists the local investigator should inform the study coordination centre who will notify the Chief Investigators. The pharmaceutical companies and/or other clinicians may be asked to advise in some cases.

In the case of discrepant views on causality between the investigator and others, all parties will discuss the case. In the event that no agreement is made, the MHRA will be informed of both points of view.

15.3 REPORTING PROCEDURES

All adverse events should be reported. Depending on the nature of the event the reporting procedures below should be followed. Any questions concerning adverse event reporting should be directed to the study coordination centre in the first instance. A flowchart is given below to aid in the reporting procedures.

15.3.1 Non serious AR/AEs

All such toxicities, whether expected or not, should be recorded in the toxicity section of the relevant case report form and sent to the study coordination centre within one month of the form being due.

15.3.2 Serious AR/AEs

Fatal or life threatening SAEs and SUSARs should be reported on the day that the local site is aware of the event. The SAE form asks for nature of event, date of onset, severity, corrective therapies given, outcome and causality (i.e. unrelated, unlikely, possible, probably, definitely). The responsible investigator should sign the causality of the event. Additional information should be sent within 5 days if the reaction has not resolved at the time of reporting.

SAEs

An SAE form should be completed and faxed to the study coordination centre for all SAEs within 24 hours. However, relapse and death due to <condition>, and hospitalisations for elective treatment of a pre-existing condition do not need reporting as SAEs.

SUSARs

In the case of suspected unexpected serious adverse reactions, the staff at the site should:

Complete the SAE case report form & send it immediately (within 24 hours, preferably by fax), signed and dated to the study coordination centre together with relevant treatment forms and anonymised copies of all relevant investigations.

Or

Contact the study coordination centre by phone and then send the completed SAE form to the study coordination centre within the following 24 hours as above. The study coordination centre will notify the MHRA, REC and the Sponsor of all SUSARs occurring during the study according to the following timelines; fatal and life-threatening within 7 days of notification and non-life threatening within 15 days. All investigators will be informed of all SUSARs occurring throughout the study.

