The safety profile of [^{18}F]-FET- β AG-TOCA as a single microdose study in rats was assessed by a commercial GLP laboratory in accordance with MHRA/EMEA guidelines (see attached). There was no tracer (or precursor) related toxicity at 1000x the intended human dose. Rat radiation dosimetry studies, conducted by GE Healthcare are complete. The radiotracer showed a suitable organ dose profile. The new fluoroethyltriazole-[Tyr]³-octreotate radioligand, FET- β AG-TOCA, combines high specific binding with rapid target localization for high contrast PET imaging.

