8. STUDY OUTLINE

8.1 Study design and rational of the chosen approaches

The total sample size will be 56 patients. Patients from cohort 1 (n=8-12), 4-6 female and 4-6 male (each cohort minimum 3) will be used in the final analysis. Patients with locally advanced or metastatic NETs of any site will be recruited from the Endocrinology, Surgical and Oncology Outpatients clinic, Hammersmith and Royal Free Hospitals. After obtaining informed consent, eligible patients will have blood taken at baseline for FBC, EUC, LFTs (routine clinical practice), and serum biomarkers. Patients will undergo routine staging. In addition, patients will undergo $[^{18}\text{F}]\text{-FET-}\beta\text{AG-TOCA}$ PET/CT scanning at Imanova. Patients' original diagnostic tumour biopsy (paraffin fixed) will be obtained.

8.1.1 Cohort 1. Dosimetry and safety study in patients with histological diagnosis of NETs of any site.

In this initial evaluation patients presenting for routine staging will be consented to undergo whole body dynamic scanning (multiple whole body scans up to 3.5 hours) with metabolite analysis in order to develop a suitable protocol for static scanning that will be used for patients in cohort 2. We will also calculate the internal radiation dosimetry, which may alter the administered dose in subsequent studies. Although we do not expect any toxicity, we will conduct detailed safety assessment in this group of patients. We require a minimum of 8 patients for final Dosimetry and safety analysis, which should include a minimum of either 3 male or 3 female subjects. To ensure both sexes are sufficiently represented in the final Dosimetry, for calculating effective dose, Cohort 1 will therefore include a minimum of 8, but up to 12 subjects.

8.1.2 Cohort 2. Open label study assessing tumoural uptake of $[^{18}\text{F}]\text{-FET-}\beta\text{AG-TOCA -PET}$ in patients with histological diagnosis of NETs of any site.

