13. COMPLICATIONS AND RADIATION DOSE

13.1 Complications

All patients will be recruited strictly according to protocol following the principles of the Declaration of Helsinki. All inclusion criteria would be satisfied before approaching patients. There are no immediate complications of the PET scan except for a potential mild bruising at the site of insertion of the cannula which should resolve in 1-2 weeks.

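### Two unadapted template sentences in the safety-reporting rules leave the deaths exempt from SAE reporting undefined and misstate which events count as expected

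*Combined protocol and SAP*

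**What the plan says.** **Reporting of deaths.** Section 15.1 counts any untoward occurrence that results in death as an SAE, and Section 15.3 wants every adverse event reported. Section 15.3.2 begins: "Fatal or life threatening SAEs and SUSARs should be reported on the day that the local site is aware of the event". Under its SAE subheading it asks for a form on every SAE within 24 hours, then adds, as an exception, that "relapse and death due to <condition>, and hospitalisations for elective treatment of a pre-existing condition do not need reporting as SAEs". The same section says that the SAE form records causality on a five-step scale and that the responsible investigator signs it.

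**Expectedness.** Section 15.2 opens by saying that most adverse events and adverse drug reactions, "whether they are serious or not, will be expected treatment-related toxicities due to the drugs used in this study". Elsewhere the plan takes a different view:

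- Section 8.1.1, on cohort 1: "Although we do not expect any toxicity, we will conduct detailed safety assessment in this group of patients".
- Section 5.2, on the rat study: "There was no tracer (or precursor) related toxicity at 1000x the intended human dose".
- Section 13.1, more narrowly: "There are no immediate complications of the PET scan except for a potential mild bruising at the site of insertion of the cannula".
- Section 15.1 calls a reaction unexpected when its nature or severity does not match the applicable product information, for example the investigator's brochure.

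**The concern.** This is a Phase 1 study that takes a new tracer into humans (Synopsis; Section 5.1). Treatment-emergent adverse events are its safety endpoint (Section 6.3), and SUSARs are among the stated grounds for halting recruitment (Section 17.5). The reporting rules therefore have to be usable as written.

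The first sentence cannot be applied as it stands, because no site can tell which deaths are exempt. It also creates an awkward order of decisions. To use the exemption, a site must already have decided what caused the death, yet the graded and signed causality judgement belongs to the form that the exemption removes.

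The second sentence stands at the head of the section on assigning causality. It tells investigators to anticipate treatment toxicity in a study that otherwise anticipates none. Expectedness decides whether a serious suspected reaction is a SUSAR, so a wrong steer here bears on regulatory notification.

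**Working it through.** The check is textual. The plan's one safety precision figure is reproduced for scale only.

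**1. A death attributed to the disease, followed through the rules.**

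- Section 15.1: it is an SAE, because it results in death.
- Section 15.3: it is to be reported, like every adverse event.
- Section 15.3.2, opening sentence: it is to be reported the same day.
- Section 15.3.2, SAE subheading: it is exempt if it is due to a condition that is not named.
- Section 15.3.1: not applicable, since that section covers only non-serious events.

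The last three steps leave such a death with a same-day duty and an exemption from it, and no other expedited route. Filling the field with NET is the natural reading in a NET-only trial, but the text does not say so. The word relapse also fits poorly, because Section 9.1 admits only locally advanced or metastatic disease.

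**2. The opening of 15.2 beside the rest of the plan.** It predicts that most events will be anticipated toxicities of the drugs, in the plural. The study gives one tracer, once. Section 8.1.1 expects no toxicity, and Section 5.2 reports none related to the tracer at 1000 times the intended human dose in rats. These statements cannot all hold. Section 13.1 is weaker support, because it concerns only immediate complications of the scan. Section 15.1 supplies the operative test, the product information, and 15.2 does not refer to it.

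**3. Scale.** Section 14.1.1 gives a maximum half-width of 0.25 at N = 12. The exact (Clopper-Pearson) 90% interval, maximised over 0 to 12 events, gives 0.2547, so the figure reproduces. Nothing in this point alters it.

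To show what one event means in cohort 1 at its full size of 12:

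- One event is 1/12 = 8.3%.
- With 0 of 12, the exact two-sided 95% upper limit is 1 − 0.025^(1/12) = 0.2646, or 26.5%.
- With 1 of 12, the upper limit solves (1 − p)^12 + 12p(1 − p)^11 = 0.025, giving p = 0.3848, or 38.5%. The lower limit is 1 − 0.975^(1/12) = 0.0021, or 0.2%.

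These are hypothetical counts. They show the sensitivity of a small cohort to one event and do not estimate how many events would be misrouted.

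**4. Exposure time.** Screening lasts up to 30 days, followed by one scan day in cohort 2 or follow-up to 24 hours in cohort 1 (Tables 2 and 3). Section 9.1 requires life expectancy above 3 months. Few disease deaths should fall within participation.

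**The case against.** The strongest reply is that this is drafting. Section 15.3.2 can be read as a rule with an exception, the missing word is almost certainly NET, and exempting disease deaths is not wrong in itself. The opening of 15.2 is a prediction, not an instruction. The working text after it has the investigator assign causality, sends doubts to the coordination centre, and takes unresolved disagreement to the MHRA. All of that is fair. It does not supply the missing definition, restore the signed causality assessment, or make the prediction agree with the rest of the plan.

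Three stronger readings are tempting, and the documents do not support them.

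- **A reader might infer that a death put down to NET vanishes from the trial.** It does not. The exemption concerns SAE reporting only. Events are collected throughout participation (footnotes to Tables 2 and 3), Section 10.2 records the reason for non-completion, and the SUSAR procedure has no such exemption.
- **A reader might infer that a serious reaction miscalled expected would miss the 7- or 15-day notification.** A non-exempt SAE still reaches the coordination centre within 24 hours, whatever the site thinks of its expectedness. The centre makes the notifications, with Section 15.1 as the test. Nor is this route the only safeguard: cohort 1 has ECG monitoring, repeated vital signs and bloods, and an overnight stay, and Section 17.5 names serious emerging effects separately from SUSARs.
- **A reader might infer that NET deaths are the hardest to separate from tracer effects.** Section 5 describes secretion by the tumours and Section 5.2 describes binding affinity in vitro. Neither links the tracer to hormone release or to deaths.

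The causality table and the reporting flowchart are not in the available text. Their absence is not counted against the plan, but they might clarify how sites route events.

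**Conclusion.** The point holds as a defect in two operative sentences and should be corrected. The SAE exemption is undefined and unreconciled with the same-day rule, and it takes away the graded and signed causality judgement on the deaths that it covers. The opening of 15.2 contradicts Sections 8.1.1 and 5.2 and is at odds with the expectedness test in 15.1.

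The text governs all 56 planned patients, but the practical effect is probably small. It is a risk of misrouting or misclassifying a rare serious event, and no loss has been shown. This rests on three assumptions: that the current text is what sites follow, that the unseen table and flowchart do not already resolve the conflict, and that short participation keeps disease deaths few. The last assumption also weakens the case for keeping the exemption, since it would save very little work.

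**What to change.** Amend two sentences.

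1. **Section 15.3.2.** Reconcile the exemption with the same-day rule. The simplest way is to remove the exemption for relapse and for death due to the unnamed condition, so that any death during participation goes on an SAE form with a causality assessment. Keep the exemption for elective hospitalisation. If the sponsor prefers to retain a disease-death exemption, it should at least name the condition, say how the exemption relates to the same-day rule, and say where causality is assessed and signed.
2. **Section 15.2.** Replace the first sentence with one that agrees with 8.1.1 and 15.1: no tracer toxicity is anticipated, and expectedness is judged only against the applicable product information.

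The cost is one protocol amendment and possibly a few extra SAE forms. No sample size, endpoint or analysis changes.

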16. DATA MANAGEMENT

Data will be collected on electronic CRFs.

17. ADMINISTRATIVE AND LEGAL CONSIDERATIONS

To ensure compliance of this trial with Good Clinical Practice (GCP) principles, the following procedures will be followed by the Investigators.

17.1 Pre-Trial Requirements

Treatment within this study will only start if the following prerequisites have been fulfilled and documentation is at hand:

Signed copy (original) of the approved protocol
EC approval of the protocol, consent form and information sheet
Approval / notification of local authorities
The Investigator will hold an Investigator's File containing the relevant study documents.

17.2 General Legal Requirements

The study will be conducted in agreement with the following directives and guidelines:

- The Declaration of Helsinki (version of Edinburgh, Scotland, October 2000)
- The respective guidelines of the European Community: Guideline for Good Clinical Practice (Note for Guidance on Good Clinical Practice / ICH E6)
- Statutory Instrument 2004 No. 1031 – The Medicines for Human Use (Clinical Trials) Regulations 2004 as amended.

All clinical work conducted under this protocol will be subject to Good Clinical Practice rules. This includes an inspection by health authority representatives at any time. The Investigator agrees to the inspection of study-related records by health authority representatives and/or the sponsor.

17.3 Protection of Subjects

17.3.1 Ethics Committee

The protocol and a copy of the subject information and informed consent form will be submitted to the competent EC(s). Written approval of the protocol and the proposed information and consent form will be obtained prior to the start of the trial.

17.3.2 Informed Consent

It is the Investigator's responsibility to explain to each subject the study procedure, potential benefits and hazards of trial participation, the right to withdraw from the study at any time, and to obtain written informed consent prior to any study-specific procedures. The original copy of the signed and dated Informed Consent Form must be filed in the patient's notes. The subject, the subject's legally authorized representative, or both will be given a copy of the

signed and dated Informed Consent Form.

17.3.3 Privacy protection

In order to maintain subject privacy, all CRFs, study drug accountability records, study reports and communications will identify the subject by initials and the assigned subject number.

The investigator will grant monitor(s) and auditor(s) access to the subject's original medical records for verification of data gathered on the CRFs and to audit the data collection process. The subject's confidentiality will be maintained and will not be made publicly available to the extent permitted by the applicable laws and regulations.

17.4 Protocol Amendments

The protocol must be read thoroughly and the instructions must be followed exactly.

Any changes in the protocol will require a formal amendment. Such amendments will be agreed upon and approved in writing by the Principal Investigator. Amendments to the protocol will be submitted to the relevant authorities and the EC for approval prior to implementation.

Administrative changes which have no significant impact on the medical or scientific validity of the study will be documented in a statement. The EC will be notified of administrative changes, if applicable.

17.5 Premature Termination of the Trial

The Investigator reserves the right to terminate the trial for well-documented reasons. Instructions will be provided in a separate document should it be determined that assessments beyond those defined by the protocol are required.

Further recruitment of subjects will not take place under the following conditions:

- Premature termination of the trial.
- Drug-related events, i.e. SUSARs, emerging adverse effects that are serious and the risk/benefit ratio is unacceptable.
- Procedure-related events, i.e., the recruitment rate is too low or the number of dropouts for administrative reasons is too high.

An 'End of Trial Form' must be completed for each subject who completes the study or who withdraws prematurely from this study.

17.6 Record Retention

After the end of study, the Investigator will maintain all site study records in a safe and secure location. The records will be stored in a location allowing easy and timely retrieval when needed (for example, for an audit or inspection). Where permitted by local regulations or institutional policy, some or all of these records may be maintained in a format other than hard copy (for example, in an electronic format), but caution should be exercised. The Investigator will ensure that all reproductions are legible and are a true and accurate copy of the original. All study records must be retained for at least 2 years after the last approval of a marketing application in an ICH region and until (1) there are no pending or contemplated marketing applications in an ICH region; or (2) at least 2 years have elapsed since the formal discontinuation of clinical development of the IP. The PI/institution should retain subject identifiers for at least 15 years after the completion or discontinuation of the study. Subject files and other source data must be kept for the maximum period of time permitted by the hospital, institution or private practice, but not less than 15 years. These documents should be retained for a longer period, however, if required by the applicable regulatory requirements. The PI must be notified and will assist with retention should institution be unable to continue maintenance of subject files for the full 15 years. It is the responsibility of PI to inform the institution as to when these documents no longer need to be retained.

If an Investigator moves, withdraws from an investigation, retires, requests to move records to another location or to assign these records to another party or (e.g. other Investigator) who will accept the responsibility, written notice of this transfer must be made to and agreed upon by each party.

17.7 Study Monitoring

The Investigator is responsible for ensuring that the study is monitored appropriately in order to ensure compliance with GCP and local regulatory guidelines. The monitor will check the completeness of medical records, verify the accuracy of entries in the CRF, and ensure adherence to the protocol and compliance with local regulatory requirements.

17.8 Final Report

A final integrated report will be prepared under the responsibility of the Investigator(s). It will include the tabulated raw data and the biostatistical report on the data.

